If a medical adverse event should occur, study staff includes two physicians who are board-certified in psychiatry (Drs. [name] and [name]). Additional medical assistance will be available through the VA TMS clinical roll-out staff RN's and physicians trained in TMS safety and adverse event management, and VA Palo Alto HCS Emergency Department service is readily available, if needed. Immediate psychiatric/psychological consultation will available for participants if required ([name]: Licensed Clinical Psychologist and [name]: Board Certified Psychiatrist). Appropriate referrals will be made when necessary in the judgment of the PI/PD or study physician.

g) Lead Investigator or Coordinating Institution in Multi-site Study.

Please explain (i) your role in coordinating the studies, (ii) procedures for routine communication with other sites, (iii) documentation of routine communications with other sites, (iv) planned management of communication of adverse outcomes, unexpected problems involving risk to participants or others, protocol modifications or interim findings.

1. Purpose

a) In layperson's language state the purpose of the study in 3-5 sentences.

The purpose of this study is to evaluate the efficacy of intermittent theta burst (iTBS) transcranial magnetic stimulation (TMS) as a treatment for Veterans with an alcohol use disorder (AUD) to decrease the exceedingly high rate of relapse associated with this condition.

b) State what the Investigator(s) hope to learn from the study. Include an assessment of the importance of this new knowledge.

At least 60% of those with AUD will experience a major relapse period within 6 months of treatment, irrespective of the intervention

(psychosocial and/or pharmacological) employed. Consequently, the high prevalence of AUD and relapse following treatment in Veterans is associated with substantial resource allocation and costs for the DVA Health Care System. Current pharmacological and psychosocial interventions demonstrate only a moderate level of efficacy, which is reflected in the high rate of relapse in AUD.

iTBS-TMS is a neurostimulation method that is at the forefront of innovative, non-invasive, and safe treatments for AUD, and the disorders that commonly co-occur with AUD. To reduce the high rate of relapse in Veterans with AUD, it is necessary for interventions to more effectively address the associated neurobiological dysfunction and salient co-occurring conditions.

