Post-Treatment Phase: Within 3-4 days of completion of the Treatment Phase, all participants will repeat neurocognitive assessment, select psychiatric assessment measures, select alcohol and substance questionnaires, 3 Tesla Magnetic Resonance Neuroimaging and blood draw as described above in Baseline/Pretreatment Assessment. Monthly Follow-ups: For the 6 months following completion of the treatment phase, participants will be contacted monthly, via telephone or in person, to complete a brief standardized measures of alcohol and substance use, as well as craving to assess for changes in these variables over the preceding 30 days. These brief contacts will be 15-20 min in duration and tracking sobriety is the primary outcome measure of this study.

b) Explain how the above research procedures are the least risky that can be performed consistent with sound research design.

All procedures will be performed by staff trained specifically for the tasks for which they are responsible. All procedures, including the iTBS-TMS, are considered low-risk procedures. iTBS-TMS is regarded as safe and without lasting side effects when established

guidelines are followed. The primary serious adverse event associated with transcranial magnetic stimulation procedures are seizures,

however, the estimated prevalence is very low at < 1%. In the case of transcranial magnetic stimulation-seizures, all have occurred during stimulation, there was no recurrence of seizures, and no incidences of status epilepticus. There have been no significant adverse cognitive, brain structural, neurologic or cardiovascular sequelae reported as a result of iTBS-TMS. Seizure risk will be minimized by careful patient selection (by rigorously screening and exclusion of participants with history

of seizure disorders or other conditions and medication use that increases risks of seizure). A seizure protocol is in place to avoid participant injury in the event that a seizure does occur (attached). Overall, the risks to participants in this proposal are reasonable in relation to anticipated benefits, if any, to the participants, and the importance of the knowledge that may be expected to result.

c) State if deception will be used. If so, provide the rationale and describe debriefing procedures. Since you will not be fully informing the participant in your consent process and form, complete an alteration of consent (in section 13). Submit a debriefing script (in section 16).

N/A

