Participants will not be compensated for study screening. Participants will receive \$15/hour for all baseline and treatment phase and week 5 follow-up study procedures. Participants will receive \$15 for each monthly contact from week 9 – 25. Those who complete all study phases will receive a \$50 completion bonus. Total possible compensation over 6 months = \$387. This rate of compensation is commensurate with other AUD research being conducted at the VA Palo Alto and VA San Francisco. Participants will be provided with a choice of an equivalent monetary amount in gift certificates to VA Palo Alto HCS Canteens, to an easily accessible department store chain (e.g., Ross), or Amazon. NO CASH or CHECKS WILL BE DISPENSED. The PI employed this procedure for 15 years at the VA San Francisco HCS to allow participants to purchase much needed fundamental clothing and other personal items, with no history of adverse events. The gift certificates are intended to facilitate participation without adding undue influence.

l) Costs. Please explain any costs that will be charged to the participant.

No costs will be incurred by any participant.

m) Estimate the probable duration of the entire study. Also estimate the total time per participant for: (i) screening of participant; (ii) active participation in study; (iii) analysis of participant data.

(i) Probable duration of study = 2 years.

(ii) Total time per participant:

Study Phase	Estimated Participation Time
Screening	20-30 min
Baseline	6.5 hours, 2 hours/day over 1 week.
Treatment	10 hours, 1 hour/day, over 2 weeks
Follow-up	Week 5 4 hours typically over 2 days
Follow-up Weeks 9 – 25	2 hours

Total Active Participation Time = approx. 22.5 hours over 6 months.

All procedures will be conducted before or after normal ATS clinic hours, or during lunch break, to not interfere with the patient's treatment schedule. The project will be conducted at the VAPAHCS MIRECC, which is on the same campus as the FOR program.

(iii) Analysis of participant data after breaking of blind will be conducted over the ensuing 6-9 months.

9. Risks

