Statistical Approach: Primary Hypothesis 1a will be tested with binary logistic regression. The criterion/dependent measure is relapse status (abstained or relapsed during the 6 months after last iTBS-TMS session). Treatment group (active iTBS-TMS vs. control) is the target predictor, and covariates will include age and composite neurocognitive functioning (based on demographically adjusted RBANS total score) as these variables may account for both within and between subject group variance. PTSD severity (based on PCL-5 total score), substance use severity (based on NIDA Drug Survey composite score), depression severity (based on BDI total score), and/or smoking severity (based on pack-years) will be considered as covariates if, after random assignment, there are post-hoc differences between treatment groups on these variables following breaking of the blind.

1b) Veterans who receive active iTBS-TMS treatment for AUD will demonstrate a significantly greater duration of abstinence in the 6 months following treatment than controls.

Statistical Approach: Primary Hypothesis 1b will be tested with Cox regression. The criterion/dependent measure is duration of abstinence after final iTBS-TMS session, and covariates include those listed for Primary Hypothesis 1a.

Secondary Hypothesis:

In the active iTBS-TMS group, Veterans with: (a) lower Glu concentration, (b) lower perfusion (blood flow), and (c) smaller volume of the left DLPFC at baseline will demonstrate a longer duration of abstinence over 6 months post treatment.

Confirmation of this hypothesis will indicate that participants who exhibit lower baseline Glu concentration, lower perfusion (blood flow), and/or smaller left DLPFC volume, and receive active iTBS-TMS, demonstrate the most robust iTBS-TMS treatment response because iTBS-TMS addresses these key neurobiological deficits that are associated with increased relapse risk. Confirmation of this hypothesis will advance our understanding of the neurobiological characteristics that predict the greatest benefit from iTBS-TMS at entry into treatment for AUD.

Statistical Approach: The Secondary Hypothesis will be tested with generalized linear mixed modeling or linear mixed modeling, depending on the distribution of the dependent measure. Duration of abstinence is the dependent measure.

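### The monthly contacts look back a fixed 30 days with no catch-up recall, so a missed or late contact leaves days unasked and can leave relapse status (1a) undetermined and duration of abstinence (1b) only bounded or dated late

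*Combined protocol and SAP*

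**What the plan says.** Section 2(a) describes the follow-up twice, in item 6 of the Protocol Summary and under Monthly Follow-ups in the detailed part: "For the 6 months following completion of the treatment phase, participants will be contacted monthly, via telephone or in person". The instruments are not named. Their stated purpose is "to assess for changes in these variables over the preceding 30 days". The same paragraphs say of these contacts that "tracking sobriety is the primary outcome measure of this study".

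The Statistical Analyses Plan takes both primary outcomes over the whole six months. For 1a (logistic regression) the outcome is "relapse status (abstained or relapsed during the 6 months after last iTBS-TMS session". For 1b (Cox regression) it is "duration of abstinence after final iTBS-TMS session".

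Section 8(k), on payment, refers to a payment "for each monthly contact from week 9 – 25". That fits four-weekly contacts, but the spacing is not stated.

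The visible text has no contact window, make-up contact, recall back to the last completed contact, or rule for missing outcomes or censoring. Other sources do not fill a gap. The breath and urine screens in section 9(c) belong to the two-week treatment phase. One further alcohol assessment falls a few days after treatment ends. Relapse disclosed during follow-up is mentioned in section 9(c) only as a reason to refer the participant back to care.

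**The concern.** 1a asks whether any relapse occurred in six months, and 1b asks when abstinence ended. Both need every day covered. A fixed 30-day window gives that only if each contact is completed about on time.

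Take a participant who misses contact 3 and answers contact 4. Under the stated window, contact 4 asks about month 4, and month 3 is never asked about. A lapse confined to month 3 reads as abstinence. Drinking that began in month 3 and continued is first seen at the start of the month-4 window, up to about a month late. Such a participant looks fully followed, so the error is easy to overlook.

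If a fraction f of relapsers is recorded as abstinent in both arms, the recorded risk difference is (1 − f) times the true one and the odds ratio moves toward 1. If f differs between arms, the comparison is biased. With 20 participants per arm, a few events matter.

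**Working it through.** The plan gives no missed-contact rate, dropout rate or power calculation, so there is no figure of its own to reproduce.

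**Inputs from the documents.** Window of 30 days; monthly contacts for six months (section 2(a)); contacts in weeks 9 to 25 (section 8(k)), used here only to suggest a spacing; 40 participants, 20 per arm. Section 1(b) gives the relapse figure: "At least 60% of those with AUD will experience a major relapse period within 6 months of treatment". That is a background statement, not a design assumption.

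**Assumptions.** Spacing of either 365.25/12 = 30.44 days or 28 days; constant monthly hazard; 5%, 10% or 20% of contacts missed, independently of drinking.

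**1. Days left unasked** = days since the last completed contact − 30.

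| Event | Calendar month | Four-weekly |
|---|---|---|
| All on time | 30.44 − 30 = 0.44 per interval | 28 − 30 < 0, none |
| One contact missed | 60.88 − 30 = 30.9 | 56 − 30 = 26 |
| 2 days late | 2.4 | 0 |
| 7 days late | 7.4 | 5 |

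**2. What one missed contact does to 1a**, if it is equally likely to be any of six. Participants who never relapse (40%) report no drinking anywhere, so their status is open. Those whose first relapse falls in the unasked month (60%/6 = 10% on average) join them if no drinking is reported later. 1a is therefore undetermined in 40–50% of such participants. In the other 50–60%, drinking reported in another window settles it. With 40% relapse the undetermined share is 60–67%; with 75% it is 25–38%.

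**3. What it does to 1b.** The duration is untouched if relapse came before the gap. With monthly hazard 1 − 0.4^(1/6) = 0.1416, the probability of relapse before months 1 to 6 is 0, 0.142, 0.263, 0.368, 0.457 and 0.534, averaging 0.294. In the other 71% or so, the duration is bounded by the gap or dated late.

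**4. First relapses that begin in an unasked month**, for contacts 1 to 5, which have a later scheduled contact. Relapse by month 5 = 1 − 0.4^(5/6) = 0.534, and 0.534 × 40 = 21.4. Multiplying by 0.05, 0.10 and 0.20 gives 1.1, 2.1 and 4.3. With 40% relapse at six months (0.347 by month 5) the range is 0.7 to 2.8; with 75% (0.685) it is 1.4 to 5.5.

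**5. Participants with at least one missed contact among the first five** = 1 − (1 − p)^5 = 0.23, 0.41 and 0.67, or 9.0, 16.4 and 26.9 of 40. Applying the 40–50% from step 2, and treating each as having one gap, 1a would be undetermined in about 3.6–4.5, 6.6–8.2 and 10.8–13.4 of 40.

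**The case against.** The strongest reply is that the text is a summary in an ethics application. The form asks applicants to refer to an attached protocol rather than copy it, and that attachment is not visible. The instruments are unnamed, and the 30-day phrase may state a purpose matched to a monthly call rather than a limit on what is asked. Sections 1(b) and 3(a) show that coverage of the full six months is intended. This stands in part: a longer look-back is not excluded. But none is written, and 30 days is the only window given for the contacts that supply the primary outcome.

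A reader might infer more than the documents support:

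- **That one missed contact makes 1a and 1b underivable.** It does not. Drinking reported in any other window settles 1a, and a relapse before the gap leaves 1b intact. Other durations are bounded and could be treated as interval-censored, although the plan does not say so.
- **That perfect attendance still falls short, because 6 × 30 = 180 days.** The shortfall is about 2.6 days on calendar months. On-time four-weekly contacts leave no days between them, because the windows overlap by 2 days.
- **That 1 to 4 participants would be misclassified in 1a.** The figure counts onsets in unasked months. Only a lapse that ends within the gap, with no later drinking reported, is miscoded, and the documents do not allow that number to be calculated.
- **That drinkers, or one arm, would miss more contacts.** This is plausible but undocumented, and the point does not depend on it.

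**Conclusion.** The point holds in this limited form. The stated window leaves about 26 to 31 days unasked after a missed contact and roughly the days of lateness after a late one (none up to 2 days late on a four-week schedule). The loss falls on participants with no drinking reported elsewhere (1a) and on those with no relapse before the gap (1b).

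Its size rests on assumptions: miss rates of 5–20%, constant hazard and a 60% relapse rate borrowed from the background. No effect on the active–sham contrast can be quantified from the documents.

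The matter goes beyond missing detail, because no analysis can recover days that were not asked about, and these contacts are the only stated source for both primary outcomes over the months after the post-treatment visit.

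**What to change.** In section 2(a), in item 6 of the Protocol Summary and under Monthly Follow-ups, replace the 30-day window for alcohol and substance use with: *since the last completed contact (or the last iTBS-TMS session)*. Use a calendar method and record the date of first drink. Keep 30 days for craving if its instrument requires it. In the Statistical Analyses Plan, state that 1a and 1b are derived from this continuous record.

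Unasked days then fall to zero whenever a later contact is completed. A missed final contact is not repaired: censor 1b at the last completed contact, and state how 1a is handled when no drinking had been reported by then.

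The cost is a sentence in each of the two places, a line in the analysis plan and a revised contact script. The downside is a slightly longer contact and recall beyond 30 days after a miss. Less precise recall is still better than having no information for those days.

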4. Treatment Phase: iTBS-TMS. Active iTBS-TMS Treatment Group – will receive a total of 20 treatments delivered 5 days/week, two treatments per day, over 2 consecutive weeks. Sham Treatment group will receive the same frequency and duration of treatment, without actual administration of iTBS-TMS. The majority of participants will be recruited from residential treatment programs; therefore, 24 hour monitoring for any adverse events will be in place as an additional layer of participant safety.

5. Post-Treatment Phase: Within 3-4 days of completion of the Treatment Phase, all participants will repeat neurocognitive assessment, select psychiatric assessment measures, select alcohol and substance questionnaires, 3 Tesla Magnetic Resonance Neuroimaging and blood draw. During this time, all participants will be receiving treatment-as-usual at the VA clinics, and scheduling of iTBS-TMS will be arranged as not to interfere with their daily curriculum.

6. Monthly Follow-ups: For the 6 months following completion of active/sham iTBS treatment, participants will be contacted monthly, via telephone or in person, to complete brief standardized measures of alcohol and substance use, as well as craving to assess for changes in these variables over the preceding 30 days. These brief contacts will be 15-20 min in duration and tracking sobriety is the primary outcome measure of this study..

DETAILS OF RECRUITMENT, DESIGN AND TREATMENT

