Design, Treatment Phase and Treatment Arms: This is a double-blind randomized group design, which will enroll 40 participants. After screening and baseline procedures, participants will be randomized to active or sham iTBS-TMS conditions (20 active, 20 sham); thus participants will have a 50% probability of receiving active treatment. Participants will receive 20 iTBS-TMS sessions over the course of 2 weeks. Participants will be required to be abstinent from alcohol and illicit substance for 7 days and demonstrate no clinically significant withdrawal symptoms prior to randomization.

Rationale for Brain Region Site: The left dorsolateral prefrontal cortex (DLPFC) was chosen as the iTBS stimulation site given excitatory transcranial magnetic stimulation to this region has been demonstrated to decrease cravings in non-Veterans with AUD. Additional stimulation of this site has been robustly shown to be associated with decreased unipolar depressive symptomatology; depressive disorders are highly comorbid in Veterans with AUD.

Duration of Treatment Phase: Active iTBS-TMS Treatment Group – will receive a total of 20 treatments delivered 5 days/week, two treatments per day (Monday-Friday), over 2 consecutive weeks. Sham Treatment group will receive the same frequency and

duration of treatment, without actual administration of iTBS-TMS. iTBS-TMS sessions will be delivered prior to the beginning of participants' treatment day, and at lunch, as to not interfere with their treatment-as-usual in the VA substance treatment clinics. There have been no adverse events reported in the literature implementing two iTBS sessions per day in any population.

Procedures for Delivery of iTBS-TMS Sessions:

1) Anatomical localization of the left DLPFC for the stimulation coil will be individualized for each participant and achieved through standardized procedures for EEG electrode placement, optimized for transcranial magnetic stimulation. The localization of participant left DLPFC will be confirmed using the subject MRI data collected prior to the treatment phase.

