Neurocognitive and psychiatric interview sessions will include breaks. In the event that a study participant appears to be under undue strain, the test or interview session will be discontinued. Participants will be reminded that they are free to withdraw from participation at any time.

iTBS-TMS administration: The iTBS-TMS operator will be the PI ([name]) and he is fully trained and qualified to administer the procedure according to current safety practices and standards of care in research and clinical settings. Co-Investigators trained in iTBS-TMS will closely monitor the iTBS-TMS PIs adherence to safety protocols and administration for this proposal. This application employs all current established and standard iTBS-TMS treatment safety and monitoring for adverse events guidelines. The iTBS-TMS operator will monitor all participants for ear protection, coil placement, and seizure activity during all sessions. All participants will be required to have abstained from alcohol or non-prescribed medication for 7 consecutive days prior to the first rTMS session. Prior to the first rTMS session, participants will be administered the Clinical Institute Withdrawal Assessment for Alcohol-Revised and must score ≤ 8 (scores > 8 are indicative of potential autonomic instability); participants with a score > 8 will immediately be escorted to their VA Palo Alto Addiction Treatment Services clinic for further evaluation. Participants will be randomly screened x6 for alcohol (breath alcohol) and substance use (urine toxicology) prior to rTMS sessions during the 2 week treatment phase. If a participant tests positive or report any alcohol or substance use during the 2 week iTBS-TMS treatment period, they will be immediately withdrawn from the study. Additionally, prior to each session, participants will complete a iTBS-TMS screen, which will include inquiring about any changes in medications or comorbid medical conditions, amount of sleep, suicide screening questionnaire prior to each rTMS session to assess for current suicide risk. Although patients in the study are regularly screened for alcohol and substance use and suicide risk while in treatment, we will conduct random alcohol/substance screening and pre-iTBS-TMS session suicide risk assessment to ensure participant welfare. Should a headache or site discomfort occur, these symptoms usually readily respond to acetaminophen or ibuprofen. Any reported painfulness typically improves over time or completely remits. To protect against possible hearing damage, participants will wear ear protection during rTMS sessions (foam ear plugs and noise attenuating headphones). This will greatly reduce the possibility of hearing loss. Hearing acuity testing pre-and-post rTMS is no longer a standard practice, given the remote likelihood of iTBS-TMS-related hearing loss.

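### Drinking during the two treatment weeks takes a randomised participant out of the study, and the plan does not say whether or how that participant enters primary analyses 1a and 1b

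*Combined protocol and SAP*

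**What the plan says.** **Order of events.** Section 2(a), Design, Treatment Phase and Treatment Arms: "After screening and baseline procedures, participants will be randomized to active or sham iTBS-TMS conditions". The two-week course of 20 sessions follows.

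**Withdrawal rule.** Section 9(c), iTBS-TMS administration: "Participants will be randomly screened x6 for alcohol (breath alcohol) and substance use (urine toxicology) prior to rTMS sessions". On a positive test, or on a report of "any alcohol or substance use during the 2 week iTBS-TMS treatment period, they will be immediately withdrawn from the study". The rule refers to the study, not only to stimulation, and covers other substances as well as alcohol.

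**Follow-up.** Section 2(a), Protocol Summary, item 6: "For the 6 months following completion of active/sham iTBS treatment, participants will be contacted monthly", and "tracking sobriety is the primary outcome measure of this study".

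**Endpoints.** SAP, Primary Hypothesis 1a (logistic regression): "relapse status (abstained or relapsed during the 6 months after last iTBS-TMS session". Primary Hypothesis 1b (Cox regression): "duration of abstinence after final iTBS-TMS session".

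**What is not stated.** For 1a and 1b the SAP gives the model, endpoint and covariates. It names no analysis set and no rule for withdrawn participants, missing relapse status or censoring. It does not define relapse beyond abstained or relapsed.

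**The concern.** Withdrawal happens after randomisation and is triggered by drinking, which is what the trial measures. If withdrawn participants are left out, membership of the analysed groups depends on the outcome, and the comparison is no longer between the groups as randomised. The bias can go in either direction, depending on how early drinking differs between arms.

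The clock adds a second problem. A participant withdrawn in week 1 does not complete treatment, which is when monthly contacts are said to start, and has a last session received but never reaches the last session scheduled. Which one is meant decides whether the early drink counts as an event.

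The SAP already leaves some covariates to be chosen after the blind is broken. An open rule on who is analysed, and how they are scored, would be another choice that could be made with results in view.

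**Working it through.** There is no plan figure to reproduce: the 40 participants are given without alpha, power, effect size or dropout. The check has two parts.

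**1. What happens to an early drinker under each reading**

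- *Withdrawn, not followed:* no outcome after the last session, so the participant drops out of 1a and adds little or nothing to 1b.
- *Followed, clock from last session received:* the problem largely goes away. Screens precede sessions and withdrawal is immediate, so a detected drink would usually fall after the last session received. The exceptions are a drink before session 1, or one missed by six screens over 20 sessions and reported after a later session.
- *Followed, clock from last session scheduled:* the drink falls before the window. A participant who is then sober for six months is scored as abstained, with no missed screen needed.

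The documents do not choose among these.

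**2. Size if early drinkers are dropped**

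Inputs: 20 per arm (plan). Total sham relapse of 60%, borrowed from the background figure in section 1(b) (at least 60%). The rest is assumed: sham early-drinking rate ps of 1%, 5% or 10%; active early rate pa equal to 0.25 or 1 times ps; later hazard halved by active; individual variation in hazard absent (SD 0) or log-normal (SD 1, both phases, integrated numerically). For placing the range only, spreading 60% evenly over 2 + 26 weeks gives 1 - exp(-2 × (-ln 0.4)/28) = 6.3% in the first two weeks.

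At SD 0:

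- sham later abstinence Ss = 0.40/(1 - ps); active Sa = √Ss
- early drinkers counted as relapsed: difference = 0.60 - [1 - (1 - pa) × Sa]
- early drinkers dropped: difference = Sa - Ss

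Example, ps = 10%: Ss = 0.4444, Sa = 0.6667, dropped = 22.22 points. With pa = 2.5%, counted = 60 - 35 = 25.00, a shift of -2.78. With pa = 10%, counted = 60 - 40 = 20.00, a shift of +2.22.

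Relapse difference (sham minus active, points), counted → dropped:

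| ps | pa/ps | SD 0 | SD 1 |
|---|---|---|---|
| 1% | 0.25 | 23.41 → 23.16 | 18.00 → 17.74 |
| 5% | 0.25 | 24.08 → 22.78 | 18.37 → 17.01 |
| 10% | 0.25 | 25.00 → 22.22 | 18.94 → 16.01 |
| 1% | 1 | 22.93 → 23.16 | 17.76 → 17.94 |
| 5% | 1 | 21.64 → 22.78 | 17.07 → 17.97 |
| 10% | 1 | 20.00 → 22.22 | 16.13 → 17.93 |

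The extremes are 16.01 - 18.94 = -2.9 and 22.22 - 20.00 = +2.2. Negative means the benefit of active treatment is understated. The standard error at 60% v 40% is √(0.24/20 + 0.24/20) = 15.5 points.

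*Scoring every early drinker as abstained* shifts the difference by -(ps - pa). At pa = 0.25 ps that is -0.75, -3.75 or -7.5 points; at equal rates it is zero. These are ceilings, since not every early drinker would later be sober.

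*One participant.* With 12/20 sham and 8/20 active relapsed, the difference is 20.0 points and the odds ratio (8/12)/(12/8) = 0.44. Dropping one early drinker from sham gives 11/19 - 8/20 = 17.9 points, odds ratio (8/12)/(11/8) = 0.48. Dropping one from active gives 12/20 - 7/19 = 23.2 points, odds ratio (7/12)/(12/8) = 0.39.

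*Chance of at least one early drinker among 40,* 1 - (1 - ps)^20 × (1 - pa)^20: 22% to 33% at ps = 1%, 72% to 87% at 5%, 93% to 99% at 10%. Withdrawals for other substances would add to these.

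**The case against.** The strongest case against is that these participants may well be followed. The paragraph of section 9 on when the experiment and individual participation end asks participants to complete the monthly assessments, directly after a sentence on subjects who withdraw. Section 2(g) expects the study to run until everyone has finished follow-up. The seizure rule in section 9(c) withdraws participants from the study yet says they will still be followed, so withdrawal need not end data collection here.

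This stands in part. A reader might infer that the plan excludes early drinkers; no text says so, and the defect is silence. But the seizure clause can equally be read as a contrast, because the alcohol rule has no such clause. Even on the generous reading, these texts secure contacts only. They do not put anyone into 1a or 1b, score the early drink or set the clock.

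A second objection is that the effect is small. That also stands: "The majority of participants will be recruited from residential treatment programs", there may be no cases, and the shifts above are far below the standard error.

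A reader might also infer a conflict over what relapse means from the phrase about a major relapse period in section 1(b). That is background on prognosis, not endpoint wording. The endpoint texts most naturally suggest any drinking, but none gives a formal definition.

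**Conclusion.** The gap is real and affects both primary analyses. A randomised participant can leave the study because of the behaviour being measured, and nothing stated keeps that participant in the analysis or fixes how the early drink is scored. It should be fixed, although the effect is probably small: about -2.9 to +2.2 points on the unadjusted relapse difference when early drinkers are dropped.

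Confidence is high on the silence of the text and low on the size. Every early-drinking rate and treatment effect used is an assumption, and the range covers only the two ratios of active to sham early drinking that were tried. The shifts are unadjusted; model 1a is covariate-adjusted, and no effect on the 1b hazard ratio was computed.

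Two stronger conclusions are tempting. One is that the rule flatters active treatment. The documents give no basis for a direction: dropping early drinkers understates the benefit if active reduces early drinking and overstates it if early rates are equal. The other is that early drinkers will be counted as successes. That needs particular circumstances, mainly follow-up with a clock from the last scheduled session, and the -7.5 point figure is a ceiling.

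**What to change.** **SAP.**

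- Analyse all randomised participants in their assigned arm for 1a and 1b.
- Before the blind is broken, fix one definition of alcohol relapse for both phases, and say whether the last session means received or scheduled.
- Count alcohol use that meets the definition between randomisation and the scheduled end of treatment as relapse. In 1b, place it at the start of the clock, entered so that the software retains it. Add a clock from randomisation as a sensitivity analysis. Other rules are defensible; the need is for one, fixed in advance.
- Do not score non-alcohol substance use alone, or drinking below the definition, as relapse. Take those participants' outcomes from the monthly contacts.
- If a withdrawn participant declines contact, censor at last contact in 1b. In 1a, apply a pre-stated missing-outcome rule with a sensitivity analysis.

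**Protocol.** Reconcile item 6 of the Protocol Summary, the alcohol and seizure withdrawal rules in section 9(c), the termination paragraph of section 9 and the SAP endpoints, so that stopping iTBS is separate from leaving the study and outcome contacts continue. No view is taken on the clinical rule for stopping iTBS.

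**Cost.** Wording, plus the monthly contacts already planned (15 to 20 minutes each) for those affected, including withdrawals for other substances. Their number is unknown, so no upper bound on staff hours is given. The downside is that the estimate will include participants who did not complete iTBS.
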